8.4.2 SERIOUS ADVERSE EVENT REPORTING

Serious adverse events must be reported to the Sponsor as soon as possible, preferably within 24 hours but in no event later than 72 hours. Any AE considered serious by the PI or Sub-investigator, or which meets the definition of an SAE included in **Definition of Serious Adverse Event** must be documented on an SAE CRF.

The Sponsor will conduct an investigation. If the Sponsor determines that the investigation presents an unreasonable risk to subjects, all investigations or parts of the investigation presenting that risk will be terminated as soon as

Apyx Medical Corporation

Protocol Number: APX-22-04-GR

Effective Date: October 2, 2023

Revision No: 04

Title: A Post-Market Study in Greece of a Minimally Invasive Lower Eyelid Treatment Utilizing the Renuvion System Clinical Trial Protocol

possible. The investigator must report serious adverse events to the reviewing IRB/FDA according to the FDA regulations.

8.4.3 UNANTICIPATED ADVERSE DEVICE EFFECT REPORTING

If an unanticipated adverse device effect occurs, the study investigator shall complete the appropriate study specific CRF and submit to the study sponsor and to the reviewing IRB as soon as possible, but in no event later than 10 working days after the investigator first learns of the effect. The study sponsor contact information is provided in **Apyx Medical Study Contact List**. The study sponsor is responsible for conducting an evaluation of an unanticipated adverse device effect and shall report the results of such evaluation to FDA and to all reviewing IRBs and participating investigators within 10 working days after the sponsor first receives notice of the effect. Thereafter the sponsor shall submit such additional reports concerning the effect as FDA requests.

8.4.4 REPORTING OF PREGNANCY

Each pregnancy that starts during the subject's study participation must be reported by the investigator to the Sponsor within 24 hours of learning of its occurrence. Pregnancies and pregnancy follow-up should be reported on an Adverse Event form. Pregnancy follow-up should describe the outcome of the pregnancy, including any voluntary or spontaneous discontinuation; details of the birth; the presence or absence of any congenital abnormalities, birth defects, maternal or newborn complications, and their relation to the device or treatment. Each pregnancy must be reported as a non-serious AE if the subject has received at least one study treatment. The following criteria should be followed:

- If a subject becomes pregnant after the Baseline visit and all study treatments have been completed, the subject should continue to be followed for the duration of the pregnancy.
- If a subject becomes pregnant after the Baseline visit but before any study treatments, the subject should be exited from the study.
- If a subject becomes pregnant after the Baseline visit but before all study treatments have been completed, additional study treatments should be discontinued, and the subject should continue to be followed for the duration of the pregnancy.

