4.3.2 PRIMARY SAFETY ENDPOINT

The primary safety endpoint is an analysis of adverse events through the D180 post-treatment visit.

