8. ASSESSMENT OF SAFETY

8.1 SPECIFICATIONS OF SAFETY PARAMETERS

8.1.1 DEFINITION OF AN EXPECTED TREATMENT EFFECT (ETE) AND AN ADVERSE EVENT (AE)

An expected treatment effect is defined as any typical treatment side-effect of the Renuvion APR System of mild to moderate severity and lasting up to a typical maximum duration. An adverse event is defined as any new medical problem, or exacerbation of an existing problem, experienced by a subject while enrolled in the study, whether or not it is considered device-related by the investigator.

An **adverse event** (AE) is any untoward or unfavorable medical occurrence in a human subject, including any abnormal sign (for example, abnormal physical exam or laboratory finding), symptom, or disease temporally associated with the subject's participation in the research, whether or not considered related to the subject's participation in the research.

Apyx Medical Corporation

Protocol Number: APX-22-04-GR

Effective Date: October 2, 2023

Revision No: 04

Title: A Post-Market Study in Greece of a Minimally Invasive Lower Eyelid Treatment Utilizing the Renuvion System Clinical Trial Protocol

A preexisting condition (one that is present at the start of the study) will be recorded as an AE only if the frequency, intensity, or the character of the condition worsens during the study period. Neither the condition, hospitalization, prolonged hospitalization, nor surgery are reported as an AE in the following circumstances: hospitalization or prolonged hospitalization for diagnostic or elective surgical procedures for a preexisting condition. Surgery should not be reported as an outcome of an AE if the purpose of the surgery was elective or diagnostic and the outcome was uneventful.

All ETEs and AEs will be collected during the conduct of this trial.

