8.1.2 DEFINITION OF SERIOUS ADVERSE EVENT (SAE)

Each adverse event should be assessed for its seriousness. The definition below should be used for this assessment. Please note that the term serious adverse event is not synonymous with a “severe” adverse event, which may be used to describe the intensity of an event experienced by the subject. (Please refer to **Section 8.2.1** for severity definitions.)

An adverse event should be classified as serious if it meets any of the following criteria:

- a. Death
Death was an outcome of the adverse event.
- b. Life-threatening
The subject was at substantial risk of dying at the time of the adverse event or use or continued use of the device.
- c. Hospitalization (initial or prolonged)
Admission to the hospital or prolongation of hospitalization was a result of the adverse event.
- d. Disability or Permanent Damage
The adverse event resulted in a substantial disruption of a person's ability to conduct normal life functions, i.e., the adverse event resulted in a significant, persistent or permanent change, impairment, damage or disruption in the patient's body function/structure, physical activities and/or quality of life.
- e. Congenital Anomaly/Birth Defect
Exposure to a medical product prior to conception or during pregnancy may have resulted in an adverse outcome in the child.
- f. Required Intervention to Prevent Permanent Impairment or Damage (Devices)
Medical or surgical intervention was necessary to preclude permanent impairment of a body function, or prevent permanent damage to a body structure, either situation suspected to be due to the use of a medical product.
- g. Other Serious (Important Medical Events)
The event does not fit the other outcomes, but the event may jeopardize the subject and may require medical or surgical intervention (treatment) to prevent one of the other outcomes.

Non-serious adverse events are all events that do not meet the criteria for a “serious” adverse event.

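### Section 8.4.4 fixes a treated subject's pregnancy as non-serious and sends its outcome to the AE form, in conflict with the SAE rules in 8.1.2 and 8.4.2

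*Combined protocol and SAP*

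**What the plan says.** Section 8.4.4 sets the scope and the clock: "Each pregnancy that starts during the subject's study participation must be reported by the investigator to the Sponsor within 24 hours". For treated subjects it fixes the classification: "Each pregnancy must be reported as a non-serious AE if the subject has received at least one study treatment". It also fixes the form: "Pregnancies and pregnancy follow-up should be reported on an Adverse Event form". The follow-up must describe, among other things, "the presence or absence of any congenital abnormalities, birth defects, maternal or newborn complications, and their relation to the device or treatment". The section states no exception for a serious outcome and does not refer to 8.1.2 or 8.4.2.

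The general safety rules read differently. Under 8.1.1 an adverse event "is any untoward or unfavorable medical occurrence in a human subject", or, in that section's other wording, a new or worsened medical problem. Section 8.1.2 asks for a seriousness assessment of each AE and keeps the non-serious class for events that meet none of its criteria. Those criteria include hospitalization (c) and congenital anomaly or birth defect (e), the latter explained as: "Exposure to a medical product prior to conception or during pregnancy may have resulted in an adverse outcome in the child". Under 8.4.2 an AE that meets the SAE definition "must be documented on an SAE CRF", and the sponsor must hear of it preferably within 24 and at most 72 hours.

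Two other sections bear on the point. Section 8.3 limits recording to events that start no later than 7 days (non-serious AEs) or 30 days (SAEs) after the last day of participation. Section 4.3.2 reads: "The primary safety endpoint is an analysis of adverse events through the D180 post-treatment visit".

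**The concern.** Section 8.4.4 settles the seriousness of a pregnancy before its outcome is known, whereas 8.1.2 makes seriousness depend on what happens. The two rules also name different forms. A site with a serious pregnancy outcome has one section telling it to use the AE form under a non-serious event, and another telling it to use the SAE CRF under a 72-hour limit. The only deadline in 8.4.4 is for notice of the pregnancy itself.

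What is at stake is mainly SAE reporting. An outcome entered as non-serious would not start the 8.4.2 notice or the sponsor investigation that follows it. There is a smaller effect on the safety summary: a pregnancy with no complication is tabulated as an adverse event although it is hard to call it untoward or a medical problem in the sense of 8.1.1, and section 10.1 has no rule that lists it separately.

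**Working it through.** The plan gives no pregnancy rate and no AE or SAE rate, so there is no figure to reproduce. The check sets the rules side by side and adds two short calculations.

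1. **Seriousness.** Take a pregnancy loss with hospital admission during participation. Under 8.1.2(c) it is serious. Under 8.4.4 a spontaneous discontinuation is part of the pregnancy follow-up, and the pregnancy must be a non-serious AE. The two rules cannot both be applied to one record. They can be reconciled only by opening a second event for the loss, which 8.4.4 does not tell the site to do.

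2. **Form.** For the same outcome, 8.4.4 names the AE form and 8.4.2 names the SAE CRF.

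3. **Birth defect.** Criterion (e) makes it serious. But 8.1.1 defines an AE as something that happens to a subject, and the child is not enrolled. The record to which the criterion most naturally attaches is the mother's pregnancy, which 8.4.4 fixes as non-serious.

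4. **Timing.** Inputs: the D180 visit falls between Day 165 and Day 195 (7.3.2 and Table 6); the SAE window is 30 days (8.3). Assumptions: participation ends at that visit, and birth comes 245 to 266 days after conception (the documents give no figure).
   - Window closes: 165 + 30 = Day 195 at the earliest, 195 + 30 = Day 225 at the latest.
   - Conception on Day 0: birth on Day 245 to Day 266, which is 20 to 41 days after Day 225.
   - Conception on Day 180: birth on Day 425 to Day 446.
   - Only a markedly preterm birth from an early conception falls inside. For example, 196 days from Day 0 is Day 196, which is in the window if the last visit is on Day 166 or later.

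   Section 8.4.4 follows the pregnancy to its end but does not say whether this extends participation. Section 5.5.1 lists pregnancy as a reason for mandatory discontinuation, so the window could close earlier still.

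5. **AE count.** With 16 treated subjects (10.2), one uneventful pregnancy adds 1/16 = 6.25 percentage points to the proportion with any AE if the subject had no other AE, and 0 points if she did. As an isolated result, 1/16 has an exact (Clopper-Pearson) 95% interval of 0.2% to 30.2%, against 0% to 20.6% for 0/16. The SAE count does not change.

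**The case against.** The best defense is that the general rules already cover the serious cases. The non-serious label is attached to the pregnancy, not to its outcome. Section 8.1.2 requires every AE to be assessed, and 8.4.2 applies to any AE that meets the definition. A serious, device-associated birth defect is also absent from the risks listed in 2.2.1, so it could qualify as an unanticipated adverse device effect under 8.1.3, with sponsor notice within 48 hours under 14.2.2. Counting every pregnancy as an AE can be seen as a deliberate reporting convention, and relatedness is recorded separately. Finally, 8.3 limits start dates, and it has events followed until they resolve or stabilize.

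Much of this stands, and it rules out several stronger readings:

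- A reader might infer that the protocol allows a birth defect to be filed as non-serious. It does not: 8.1.2(e) and 8.4.2 make it an SAE. What remains is a contradictory instruction that could lead to misfiling.
- A reader might infer that a birth defect would move the primary safety endpoint from 0/16 to 1/16 SAEs. A term birth falls after D180, so that contrast does not apply to the endpoint. It could apply only to an outcome within D180, such as an early loss with admission.
- A reader might infer that the halting rule in 8.5 would be disabled. The action there is discretionary and extends to any other perceived safety concern, so it does not depend on the SAE label.
- A reader might extend the rule to all later pregnancies. It covers only those that start during participation.

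Two parts of the defense do not answer the point. The unanticipated-effect route also depends on the outcome being recognized as serious, which is the step 8.4.4 confuses. And if a birth outcome is recorded only as follow-up of the pregnancy, it stays under the event that 8.4.4 has labeled non-serious.

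**Conclusion.** The conflict is real but minor. For a pregnancy that itself meets an SAE criterion, 8.4.4 cannot be followed together with 8.1.2 and 8.4.2 as written, and a site applying 8.4.4 literally could miss the 72-hour SAE report. If pregnancy follow-up does not extend participation, the 8.3 window closes 41 days or more before a term birth at 266 days (20 days or more at 245), and 8.4.4 is then the main route by which the outcome reaches the record.

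The effect on the AE summary is secondary: at most 6.25 points per pregnancy with 16 treated, and none if the subject already had an AE. The analysis is descriptive and has no safety threshold, so no planned decision depends on it.

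Events should be rare. There are at most 16 treated subjects of both sexes aged 18 to 75; pregnant women and those planning pregnancy are excluded; and contraception is required of sexually active women of childbearing potential. The sizes above are per occurrence, because the documents give no pregnancy rate.

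**What to change.** Replace both the non-serious-AE sentence and the AE-form sentence in 8.4.4. The new text should say that:

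- a pregnancy is notified to the sponsor within 24 hours, flagged, and tabulated apart from AEs;
- any maternal, fetal or newborn outcome that meets 8.1.1 is recorded as an AE;
- any such outcome that meets 8.1.2 is recorded as an SAE on the SAE CRF under the 8.4.2 timelines whenever it becomes known, including after the 8.3 window has closed.

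State in section 10.1 that pregnancy outcomes after D180 are reported separately from the D180 safety endpoint. Reconcile 8.4.4 with 8.3 and 5.5.1, so that the protocol says whether participation continues during pregnancy follow-up; that choice is for the sponsor.

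The cost is a wording amendment, handled under section 15.2, and a flag on the existing form. No visits, subjects or assessments are added, because 8.4.4 already follows the pregnancy for its duration.

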8.4.5 REPORTING OF DEATHS

The investigator must notify the Sponsor as soon as possible, preferably within 24 hours but in no event later than 48 hours, of learning of a subject's death, regardless of whether the death is related or unrelated to the investigational device. The investigator should attempt to determine, as conclusively as possible, whether the death is related to the device. The cause of death and the investigator's discussion regarding whether or not the death was device-related should be described in a written report. The investigator must report death to the reviewing IRB according to the IRB regulations at the study site.

8.5 STUDY HALTING RULES

This clinical trial will be halted if subjects' safety is questioned based on a reporting of severe, device-related AEs at an excessive frequency. The Sponsor and/or investigator may recommend termination or modification of the study if there is an occurrence of any device- or treatment-related Serious Adverse Event, using the clinical protocol definitions of Serious Adverse Event. In addition, termination or modification may be recommended for any other perceived safety concern based on clinical judgment, including but not limited to a severe burn (anticipated or unanticipated), a higher than anticipated rate for any component of the safety measures, device failures resulting in Adverse Events, or unexpected SAEs. The study sponsor will notify all investigators to immediately halt any

ApyXTM MEDICAL Apyx Medical Corporation	
Protocol Number: APX-22-04-GR	Effective Date: October 2, 2023 Revision No: 04
Title: A Post-Market Study in Greece of a Minimally Invasive Lower Eyelid Treatment Utilizing the Renuvion System Clinical Trial Protocol	

continuing enrollment activities and not enroll any additional study participants. The study sponsor will inform the IRB/FDA of the temporary halt and the disposition of the study.

The Sponsor and/or investigator may recommend termination or modification of the study if there is an occurrence of any device- or treatment-related Serious Adverse Event, using the clinical protocol definitions of Serious Adverse Event. In addition, termination or modification may be recommended for any other perceived safety concern based on clinical judgment, including but not limited to a severe burn (anticipated or unanticipated), a higher than anticipated rate for any component of the safety measures, device failures resulting in Adverse Events, or unexpected SAEs. Enrollment and treatment would be suspended during root cause investigation to determine the cause of the respective AE.

9. CLINICAL MONITORING

Clinical site monitoring is conducted to ensure that the rights and well-being of human subjects are protected, that the reported trial data are accurate, complete, and verifiable, and that the conduct of the trial is in compliance with the currently approved protocol/amendment(s), with GCP, and with applicable regulatory requirement(s). A study-specific Monitoring Plan will further define responsibilities and details related to clinical site monitoring.

10. STATISTICAL METHODOLOGY

10.1 STATISTICAL AND ANALYTICAL PLANS

For the purposes of this post-market study, descriptive statistics will be performed. For a given parameter, data will be summarized for each time point for which data for that parameter are available. Categorical variables will be summarized as frequencies and percentages in each category. Continuous and ordinal variables will be summarized as numbers of subjects, means, standard deviations, medians, and ranges.

An interim review and analysis of all study data through Day 90 will be completed once all subjects have passed the Day 90 visit window.

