4.3 STUDY ENDPOINTS

4.3.1 PRIMARY EFFECTIVENESS ENDPOINT

Improvement in the lower eyelid area as determined by a masked, qualitative assessment of photographs at 180-days post-treatment compared to baseline. Improvement based on 2D photographs taken at all visits using the site's photography system.

Three experienced, blinded independent photographic reviewers (IPR) will perform a qualitative analysis/review of the pre-treatment and post-treatment sets of images of each subject in a blinded and randomized order. Each blinded reviewer will choose which image is the post-treatment image. Success will be correct post-treatment image

 Apyx Medical Corporation	
Protocol Number: APX-22-04-GR	Effective Date: October 2, 2023 Revision No: 04
Title: A Post-Market Study in Greece of a Minimally Invasive Lower Eyelid Treatment Utilizing the Renuvion System Clinical Trial Protocol	

selection by at least 2 of the 3 reviewers. The percentage of subjects with a correct post-treatment image selection will be calculated.

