4.3.4.1.1 INDEPENDENT PHOTOGRAPHIC ASSESSMENTS

Three experienced, blinded photographic reviewers will perform a qualitative analysis/review of the pre-treatment and post-treatment sets of images of each subject in a blinded and randomized order. Each

Apyx Medical Corporation

Protocol Number: APX-22-04-GR

Effective Date: October 2, 2023

Revision No: 04

Title: A Post-Market Study in Greece of a Minimally Invasive Lower Eyelid Treatment Utilizing the Renuvion System Clinical Trial Protocol

blinded reviewer will choose which image is the post-treatment image. Success will be correct post-treatment image selection by at least 2 out of 3 reviewers. The percentage of subjects with a correct post-treatment image selection will be calculated.

Assessment of each subject's baseline and follow-up images viewed simultaneously will be performed by the Independent Photographic Reviewers (IPR) who will be blinded to the study subject's visit (baseline and follow-up visit). Each IPR will view each subject's randomized pre-treatment and post-treatment images and assess which set of images represent the subject's post-treatment images. Each photograph will have a unique identification number, but the sets of images will not be arranged in any specific order (i.e., randomized order). The Sponsor will prepare and administer the IPR.

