4.3.4.1.2 INDEPENDENT PHOTOGRAPHIC REVIEW EVALUATION PROCESS

Each blinded assessor will be provided with identical photos to be assessed. The pre-treatment and post-treatment photos will be consistent in lighting, subject positioning, and focus. Each photo's visit interval, i.e., pre-treatment and post-treatment, will NOT be marked. The images placement (right or left) will be randomly ordered for pre-treatment and post-treatment images. Images for each subject will be grouped together into one set with all pre-treatment and post-treatment images in the same location (right/left) for the subject set.

Each blinded assessor will conduct their assessment independently with no input from another blinded assessor.

Each blinded assessor compares the Left and Right photo for change that may be striking (substantial and immediately noticeable), readily apparent but modest in nature, or slight and subtle in nature that may require close examination. Assessors should look through each view and assess change. Enough time should be allowed to do this for each subject, so the assessments are not rushed.

The assessor chooses which photo they believe to be the post-treatment photo (i.e., Left photo or Right photo) once all images in the subject set have been reviewed.

Post-Analysis Coding of Masked Assessment:

- If the assessor incorrectly chooses the post-treatment photo, this will be coded as an "Incorrect post-treatment selection".
- If the assessor correctly chooses the post-treatment photo, this will be coded as a "Correct post-treatment selection".
- Success will be determined by correct identification of post-treatment photographs by at least two out of three blinded, independent reviewers.

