5.5.2 HANDLING OF WITHDRAWALS OR TERMINATION

The subject must undergo the recommended follow-up assessments specified for the last study visit unless contraindicated due to a medical condition. Withdrawn subjects will not be replaced.

Subjects who are discontinued from the study due to an AE(s) will be treated according to standard clinical practice and will be followed-up until the final study visit/safety visit as described in **Section 7**. All pertinent information concerning the AE will be documented on the appropriate study specific CRF.

A subject may discontinue from the study at any time without any penalty or loss of benefits to which the subject is otherwise entitled. An Investigator may also discontinue a subject from the study without the subject's consent, if the Investigator feels it is in the best medical interest of the subject. The date and the reason for study withdrawal will be indicated on the Study Exit CRF.

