7.3.2 FOLLOW-UP VISITS & SUBJECT CONTACT OUTSIDE OF FOLLOW-UP VISITS

Subjects will be asked to return to the study site at the following times post-procedure:

- 1 day
- 3(± 1) days
- 7 (± 3) days
- 30 (± 7) days
- 90 (± 10) days
- 180 (± 15) days

Post-procedure assessments and 2D photographic imaging will be performed during the follow-up visits, see **Table 6**. The same standardized photography views will be used throughout the study as documented in the image capture document developed for the study.

Due to the challenges of COVID-19, if a subject is unable to return to the office for an in-person visit, follow-up visits will be conducted virtually. If a visit is completed virtually, missing assessments such as photographs will be documented as a protocol deviation specifically noting COVID-19. Outside of photographs, study investigators and study staff will ensure all other assessments related to each follow-up visit are completed virtually if the visit is done virtually. For virtual visits, the investigator and/or study staff completing the visit and assessments will be identified on the case report form; as well, the manner in which the visit was completed will also be recorded (i.e., video call, phone call, etc.). Virtual visits should be done via video call, if possible, to ensure subject identity. If a telephone call must be done, the investigator and/or study staff must positively identify the subject prior to conducting the virtual visit by requesting the subject to state their address and date of birth. Subjects will be strongly encouraged to come in (albeit safely) for their D180 visit; this visit is vitally important as this is the primary endpoint and photographic images are needed for many of the assessments. Only investigators and study staff who have been trained and delegated to conduct virtual visits as indicated on the delegation log may conduct virtual study visits.

Subjects may be seen for an unscheduled appointment at any time at investigator's discretion.

Apyx Medical Corporation

Protocol Number: APX-22-04-GR

Effective Date: October 2, 2023

Revision No: 04

Title: A Post-Market Study in Greece of a Minimally Invasive Lower Eyelid Treatment Utilizing the Renuvion System Clinical Trial Protocol

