10.2 SAMPLE SIZE

The study will include up to 16 treated subjects from a single center in Greece.

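### The primary photographic success rate is expected to be 50% by guessing alone, but the plan states neither that reference nor an interval

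*Combined protocol and SAP*

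**What the plan says.** Section 4.3.1 names the primary effectiveness endpoint as improvement in the lower eyelid area at Day 180, judged from masked photographs. The scoring is a forced choice. Under section 4.3.4.1.2, "The images placement (right or left) will be randomly ordered for pre-treatment and post-treatment images", and then "The assessor chooses which photo they believe to be the post-treatment photo (i.e., Left photo or Right photo"). No option for seeing no difference is listed. Section 4.3.4.1.1 sets the subject-level rule: "Success will be correct post-treatment image selection by at least 2 out of 3 reviewers". Section 4.3.1 sets the summary: "The percentage of subjects with a correct post-treatment image selection will be calculated".

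Section 10.1 declares the study descriptive and says of such data that "Categorical variables will be summarized as frequencies and percentages in each category". Section 10.2 says only that "The study will include up to 16 treated subjects from a single center in Greece". Nowhere do the documents give a chance level, reference value, performance goal or confidence interval for this endpoint. The same photographic assessment at Day 90 is the first additional outcome in section 4.3.3, and it has the same gap.

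**The concern.** A percentage labelled success, on an endpoint labelled improvement, invites the reader to treat 0% as the no-effect value. For a two-way forced choice the no-effect value is 50%. Because the study has no control arm, that chance level is the only comparator built into the primary result. If the plan is followed exactly and the treatment changes nothing that can be seen, the report is expected to show about half of the subjects as successes.

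The plan also never asks for an interval. With at most 16 subjects, percentages that look persuasive are still compatible with guessing.

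A related limit affects the wording of any result. Reviewers record which photograph was taken after treatment, not which one looks better. A high percentage therefore shows that the pairs can be told apart, and improvement is a further inference.

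**Working it through.** The plan gives no figure to reproduce: 16 is stated without an error rate, power, expected success rate or target precision. The check therefore starts from the scoring rule.

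**Inputs from the documents**
- Two response options with random side placement (4.3.4.1.2)
- Three reviewers, success at two or more correct (4.3.1, 4.3.4.1.1)
- Up to 16 treated subjects (10.2)

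**Assumptions of this review**
- Pure guessing, with no cue to visit
- Independence across subjects
- A 95% confidence level
- Evaluable numbers of 12 to 15 as illustrations, because the documents give no dropout rate

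**Step 1: chance rate per subject.** Each pick is correct with probability 0.5. For the majority:

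P(2 or 3 correct) = 3 × 0.5² × 0.5 + 0.5³ = 0.375 + 0.125 = 0.500

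This does not depend on the reviewers guessing independently of one another. Random placement makes correct and incorrect symmetric, so the number correct, K, has the same distribution as 3 − K, and P(K ≥ 2) = P(K ≤ 1) = 0.5. Correlations of 0, 0.25, 0.5 and 1 between reviewers' guesses all give 0.500.

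**Step 2: expected count.** 16 × 0.5 = 8 successes.

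**Step 3: what 16 subjects can show.** The upper tail is P(X ≥ x) for X ~ Binomial(16, 0.5). The exact (Clopper-Pearson) 95% limits are the 0.025 quantile of Beta(x, n − x + 1) and the 0.975 quantile of Beta(x + 1, n − x).

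| Successes | % | P(this many or more by guessing), one-sided | Exact two-sided 95% CI | Includes 50%? |
|---|---|---|---|---|
| 10/16 | 62.5 | 22.7% | 35.4%–84.8% | yes |
| 11/16 | 68.8 | 10.5% | 41.3%–89.0% | yes |
| 12/16 | 75.0 | 3.8% | 47.6%–92.7% | yes |
| 13/16 | 81.3 | 1.1% | 54.4%–96.0% | no |

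The two yardsticks agree once the level is stated. The lower limit of a two-sided 95% interval exceeds 50% only when the one-sided tail is below 2.5%. At 12/16 the tail is 3.8%, so the interval still includes 50%. At 13/16 it is 1.1%, so the interval excludes it.

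**Step 4: fewer evaluable subjects.** Section 5.5.2 says "Withdrawn subjects will not be replaced". For visits held virtually, section 7.3.2 (follow-up visits) says "missing assessments such as photographs will be documented as a protocol deviation specifically noting COVID-19". The smallest count whose interval excludes 50% is then:

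| Evaluable n | Count | Exact two-sided 95% CI |
|---|---|---|
| 15 | 12 | 51.9%–95.7% |
| 14 | 12 | 57.2%–98.2% |
| 13 | 11 | 54.6%–98.1% |
| 12 | 10 | 51.6%–97.9% |

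At 14 evaluable, 11/14 (78.6%) has an interval of 49.2% to 95.3% and still includes 50%.

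**The case against.** The strongest reply is that the study is openly descriptive. It states no hypothesis, error rate or performance goal, so counts and percentages are consistent with its design. A reader who has the count and denominator can work out both the chance level and the interval, so nothing is lost. It is true that the plan contains no arithmetic error and no failed power claim. But an interval and a reference value are themselves descriptive reporting, and the reader must first realise that the scoring rule has a 50% chance level, which the documents never say.

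A second reply is that a rule on wording tied to a 95% interval brings a test in by the back door. It does act as a threshold on what may be said, and the 95% level is this review's choice. It sets no pass/fail criterion for the study, and its purpose is to fix the language before the data are seen.

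Three smaller points also have force.
- The summary is defined literally as correct selection, so a report keeping to that label would be accurate. However, the documents also call it success and improvement.
- Section 7.3.2 presses for in-person attendance at Day 180, so the loss of photographs may be small. The smaller-n figures are illustrations only.
- The 50% reference assumes no cue other than a treatment effect. Incision marks or photographic differences between visits could raise the rate without any improvement. This strengthens the case for caution about results above 50%.

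**Conclusion.** The concern holds and should be fixed. Under the protocol's own scoring rule, a treatment with no visible effect is expected to give 8 successes in 16, and section 10.1 requires neither that reference nor any interval to be shown. At 16 subjects and a two-sided 95% level, every result up to and including 12/16 (75%) has an interval that is compatible with guessing or worse.

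The 50% figure rests on random side placement and the absence of other cues; it does not require the reviewers' guesses to be independent of each other. The tail probabilities and intervals also assume independence between subjects. Nothing here says that the treatment has no visible effect. The point is that the planned summary does not let a reader tell a visible effect from none without work the plan leaves undone. Whether a correct pick means improvement is a separate limit, and an interval does not remove it.

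**What to change.** Add to section 10.1, for example:

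> For the Day 180 and Day 90 photographic endpoints, the number and percentage of evaluable subjects correctly identified by two or more of the three reviewers will be presented with an exact (Clopper-Pearson) two-sided 95% confidence interval, beside the 50% expected from guessing. If the interval includes 50%, the result will not be described as distinguishable from guessing. A result above 50% shows that post-treatment photographs could be identified and is not by itself proof of improvement.

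Show each reviewer's number and percentage correct in the same table, with the evaluable denominator. No pass/fail cut-off is needed. Section 10.1 plans an interim review of data through Day 90, so the text is best settled before that review.

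The cost is three sentences and some extra columns in one table, with no new data, visits or subjects. The drawback is that the reported result will look less favourable, because intervals at this sample size are wide.
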